Monitoring of Suicidal Ideation: This is a challenging aspect the study and so we have developed our procedures to be consistent with the recommendations of organizations such as NIH in clinical research in people with elevated suicide risk (e.g., Issues to Consider in Intervention Research with Persons at High Risk for Suicidality). We will further refine our procedures by use of deployment focused discussions with stakeholders in the study start up phase and in collaboration with the Data Safety Monitoring board. The referral sources for this study are VASDHS' Veterans with inactive and active high-risk suicide flags. Veterans with active high-risk suicide flags are closely monitored and regularly assessed for suicide risk by the VASDHS' Suicide Prevention Coordinator (SPCs). At baseline, participants are administered the C-SSRS55. Veterans are informed during consenting that all suicidal behavior is documented in Suicide Behavior Reports in CPRS if not already entered. If ideation exceeds a score of 2, the PI will be contacted and will perform a telephone evaluation and refer the screened potential participant to the SPCs or emergency services as necessary. Our safety monitoring guide details these procedures, how they are recorded, and what the staff, facility, and investigator responsibilities are. All Veterans are provided the contact information for the Veterans' Crisis Line. Any new suicidal behavior will be documented in the Suicide Behavior and Overdose Report in CPRS by research staff. Participants who elect to withdraw from the study will continue to receive suicide prevention services per VA San Diego's protocol. We will monitor these protocols during the course of the study and will make adjustments to inclusion/exclusion criteria or safety protocol in case of adverse events.

All research personnel will complete VA TMS trainings pertinent to suicide prevention.

Confidentiality: In order to protect confidentiality, all participant data will be de-identified by

assigning each participant a unique ID in computer files, and all physical files from the study will be kept in a locked cabinet in study offices at the Veterans Medical Research Foundation building in San Diego. All electronic data and files will be stored on a secure server. Only study investigators and personnel will have access to these data. All documentation will identify participants only by their Unique ID number and not other personally identifying information.

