15) Describe the procedures for protecting against or minimizing any potential risks/discomforts, and the adequacy of resources for conducting the study and resources participants may need as a consequence of the research. When applicable, include detail of the following safety measures: (a) The type of safety information to be collected, including AEs; (b) Frequency of safety data collection; (c) Frequency or periodicity of review of cumulative safety data; (d) Statistical tests for analyzing the safety data to determine if harm is occurring; and (e) Conditions that trigger an immediate suspension of the research. See ? for further requirements.

During the telephone screening portion of our study, risk will be mitigated by using a set of screening questions that will elicit the least amount of sensitive or personal information necessary to assess eligibility. Only qualified interviewers with significant prior experience in treatment or assessment of relevant populations/conditions will conduct these assessments. All study personnel will be trained, observed, and certified by the study's PI, who is a licensed clinical psychologist. The first three months of this study will be included focused training on assessment administration. For example, the C-SSRS has a standard series of training videos that study personnel will undergo to ensure proper administration of this instrument. Standardize trainings will take place for any instruments where this type of formal training is available.

In addition, to further mitigate risk participants will be informed that they do not have to answer any question they do not want to, and can decide, at any time, if they want to withdrawal from the study. The study PI will be available to discuss any concerns participants may have with the study.

If during the course of the study participants experience an adverse reaction during screening, assessment administration, or group participation (i.e., for card makers), imminent risk for suicide is determined, or a suicide attempt (that has not been previously recorded) is disclosed, the research team will adhere to the following to ensure Veterans' safety.

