Monitoring of Suicidal Ideation: This is a challenging aspect the study and so we have developed our procedures to be consistent with the recommendations of organizations such as NIH in clinical research in people with elevated suicide risk (e.g., Issues to Consider in Intervention Research with Persons at High Risk for Suicidality). We will further refine our procedures by use of deployment focused discussions with stakeholders in the study start up phase and in collaboration with the Data Safety Monitoring board. The referral sources for this study are VASDHS' Veterans with inactive and active high-risk suicide flags. Veterans with active high-risk suicide flags are closely monitored and regularly assessed for suicide risk by the VASDHS' Suicide Prevention Coordinator (SPCs). At baseline and follow-up, participants are administered the C-SSRS and BSS. Veterans are informed during consenting that all suicidal behavior is documented in Suicide Behavior Reports in CPRS if not already entered.

As such, if any of the following items are endorsed (respective item scores are noted below) on the Beck Scale for Suicidal Ideation (BSS) a LIP will be notified immediately:

- Item 4 (2)
- Item 9 (1 or higher)
- Item 13 (2)
- Item 14 (2)

- Item 15 (2)
- Item 16 (1 or higher)
- Item 17 (1 or higher)
- Item 18 (2)
- Item 20 (1 or higher)

If any of the following items are endorsed on the C-SSRS (initial screener):

- Item 4 (Active Suicidal Ideation with Some Intent to Act, without Specific Plan)
- If a Veteran answers "Yes" to the question about preparatory acts or behaviors within the past month - i.e., "Have you taken any steps towards making a suicide attempt or preparing to kill yourself (such as collecting pills, getting a gun, giving valuables away or writing a suicide note)?"

If any of the following items are endorsed on the C-SSRS (since last contact):

- Item 4, "Have you had any intention of acting on these thoughts of killing yourself? (As opposed to you have the thoughts, but you definitely would not act on them?)"
- Item 5, "Have you started to work out, or actually worked out, the specific details of how to kill yourself and did you intend to carry out your plan?"
- Item 6 "Have you done anything, started to do anything, or prepared to do anything to end your life?"

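### Sections 9.9 and 15 give different escalation triggers and contacts for what appears to be the same baseline C-SSRS, and do not say how they relate

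*Protocol*

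**What the plan says.** Section 9.9 of the protocol (Data Safety Monitoring Board or Plan) states "At baseline, participants are administered the C-SSRS55". Shortly afterwards it gives its rule: "If ideation exceeds a score of 2, the PI will be contacted and will perform a telephone evaluation and refer the screened potential participant". Referral is to the Suicide Prevention Coordinators or emergency services as needed. The rule names no scale, but the C-SSRS is the only instrument mentioned in that paragraph.

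Section 15 (Risk Management) introduces its procedures together, saying that "the research team will adhere to the following to ensure" Veterans' safety, and then carries nearly the same monitoring paragraph. Here the sentence on instruments reads "At baseline and follow-up, participants are administered the C-SSRS and BSS", and the score-of-2 rule is absent. Three item lists take its place:

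- **BSS.** Nine items with stated scores; if any is endorsed "on the Beck Scale for Suicidal Ideation (BSS) a LIP will be notified immediately".
- **C-SSRS, initial screener.** "Item 4 (Active Suicidal Ideation with Some Intent to Act, without Specific Plan"), or a positive answer "to the question about preparatory acts or behaviors within the past month".
- **C-SSRS, since last contact.** Items 4, 5 and 6.

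The two C-SSRS lists end without an action of their own. Both sections refer to a safety monitoring guide for procedures and responsibilities; it is not among the documents available. Neither section refers to the other.

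**The concern.** Both sections stand as current text, and both purport to say when a rater must escalate after a suicide-risk assessment. A reader of Section 9.9 finds one ideation threshold, the PI as contact and a telephone evaluation. A reader of Section 15 finds a different ideation item, a behaviour item that Section 9.9 lacks, and a LIP as the only contact named. Nothing says whether the rules add to one another, form tiers, or replace one another.

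All participants have an active or past high-risk flag. Section 9.9 describes close outside monitoring by Suicide Prevention Coordinators for the Veterans with active flags, who are to make up 50 of the 80. For the 30 card makers with inactive flags no equivalent is described, so the study's own triggers carry more of the weight. What is at stake is whether a baseline response that one section treats as requiring a contact would be passed over by someone working from the other.

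**Working it through.** There is no sample size, power or error rate to recompute. The check is a comparison of the two texts.

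**Step 1: do the rules concern the same assessment?** Section 9.9 ties the C-SSRS to baseline. The enrolment text in Section 9 places the C-SSRS in the battery given after consent. Section 9.8 lists two C-SSRS forms, and the Since Last Contact form belongs to the follow-up battery. Section 27.2 likewise distinguishes the baseline version from the follow-up version. The telephone screening questions are a separate entry in Section 9.8. The initial screener of Section 15 is therefore most naturally the baseline form, and so is the C-SSRS of Section 9.9. The closing words of the Section 9.9 rule, which speak of a potential participant who has been screened, leave some doubt.

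**Step 2: compare the C-SSRS triggers.** The documents do not define the ideation score. Assume that it is the highest ideation item endorsed, from 0 to 5. The Section 9.9 rule is then score > 2. The Section 15 rule is Item 4 endorsed, or preparatory acts in the past month.

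| Baseline response | Section 9.9 | Section 15, C-SSRS list |
|---|---|---|
| Score 0 to 2, no acts | no | no |
| Score 0 to 2, with acts | no (at most 2) | yes (acts) |
| Score 3, no acts | yes (3 > 2) | no |
| Score 3, with acts | yes | yes (acts) |
| Score 4 | yes | yes (Item 4) |
| Score 5, no acts | yes | only if Item 4 is also endorsed |
| Score 5, with acts | yes | yes (acts) |

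Each section thus triggers on a response that the other does not: row 2 for Section 15 and row 3 for Section 9.9. The score-5 row without acts cannot be settled from the text. The Section 15 item that asks whether the person has "actually worked out, the specific details of how to kill yourself and did you intend to carry out your plan" appears in the follow-up list only.

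**Step 3: compare contact and action.** Section 9.9 gives PI contact, telephone evaluation and referral. Section 15 gives immediate notification of a LIP, but in the BSS sentence. That the C-SSRS lists share this action is suggested by their position and by the common lead-in; it is not stated. The PI is described as a licensed clinical psychologist and may be a LIP, but the protocol does not say so.

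**Step 4: allow for the BSS.** Section 15 lists BSS items 4, 9, 13, 14, 15, 16, 17, 18 and 20, nine in all. Four of them (9, 16, 17 and 20) trigger at a score of 1 or higher. Some responses that escape the Section 15 C-SSRS list would be caught here. Section 9.9 has no BSS trigger, so the BSS does not help a reader of that section alone.

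**The case against.** The strongest reply is that nothing here is contradictory. Both sections belong to one protocol, neither list is declared exclusive, and a team that applies both will make every contact that either requires. That stands: a reader might infer that the two rules conflict so that one cannot be obeyed without breaking the other, and the text does not support this.

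Second, the stage is open. The Section 9.9 rule ends with pre-enrolment wording, and Section 15 also mentions standardized tools used during screening. If the rule is meant for screening only, the two rules concern different stages. This stands as a possibility. It does not dispose of the point, because Section 9.9 mentions the C-SSRS only at baseline and assigns the rule to no other stage.

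Third, the safety monitoring guide may already set out tiers and roles. It may, and for that reason nothing can be said about what staff actually did. But the guide would not make the two protocol sections agree with each other.

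Fourth, the practical reach is limited. Section 15 says that all personnel are trained, observed and certified by the PI. The form is dated 11/22/2022, and Section 4 gives 12/01/2022 as the end of the study, 9 days later; the compensation paragraph in Section 9 rules out recruitment in year two. On those dates few baseline assessments, if any, remain. This weighs on urgency. The actual timeline is not shown.

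**Conclusion.** The inconsistency is real but modest. Two versions of one monitoring paragraph state different triggers and name different contacts for what is most plausibly the baseline C-SSRS, and the protocol does not say how they relate. Under the assumption that the score is the highest ideation item endorsed, the clear differences are a score of 3 without preparatory acts (Section 9.9 only) and preparatory acts with a score of 0 to 2 (Section 15 only).

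The conclusion that the texts differ does not need the scoring assumption: Section 9.9 has no behaviour trigger and Section 15 has no score threshold. It does rest on reading the initial screener as the baseline form. If that is wrong, what remains is that the stage of the Section 9.9 rule is unclear.

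A reader might go on to infer that participants at risk were overlooked, or that a known share of the 80 is affected. The documents support neither: no response frequencies are given, the BSS triggers apply at the same visit under Section 15, and the guide is unseen. The feasibility, acceptability and pre/post analyses under Aims 1 to 3 are not touched.

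**What to change.** Reconcile the monitoring paragraphs of Sections 9.9 and 15 with each other and with the safety monitoring guide, so that both sections give the same triggers, the same stage (screening or baseline), the same contact role and the same action. The text should say how the score-of-2 rule and the item lists relate, and which scale the score refers to. Which cut-offs apply, and which action follows which trigger, is for the investigators and the IRB to decide; this review takes no position.

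The cost is a text amendment, with no procedure added by the reconciliation itself. Staff would need a briefing on the agreed wording only if baseline assessments are still being done.

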- Be compensated \$60 for each set of assessments you attend (up to \$120 total).

For more information or to sign up for this study,
contact [name] at [contact] or [contact].
You can also talk to the provider who gave you this flyer.

Providers

Caring Cards to and from Veterans: A Peer Approach to Suicide Prevention and Recovery

Researchers at the VA San Diego are studying if anonymous cards made by Veterans with a history of elevated suicide risk help Veterans with current elevated suicide risk. We are seeking referrals for card makers and recipients!

Card Makers

Inclusion criteria:

- VA San Diego Veteran with an inactive high-risk flag for suicide
- 18 years of age or older
- Access to transportation to attend groups (if held in person; groups may be held via telehealth

due to COVID-19)

- Decisional capacity

Exclusion criteria:

- Absence of a mailing address or working phone number
- Inability to read and write in English
- Previous experience as either a card maker or recipient
- Currently employed by the VA San Diego
- If groups are held via telehealth, the absence of access to reliable computer, tablet, or smartphone with camera and internet access

What would being a card maker entail?

Veterans would meet weekly for 120-minutes for six months. In the group meetings they would connect with other Veterans and anonymously create caring cards for the card recipients described below.

Card Recipients

Inclusion criteria:

- VA San Diego Veteran with an active high-risk flag for suicide
- 18 years of age or older
- Decisional capacity

Exclusion criteria:

- Absence of a mailing address or working phone number
- Inability to read and write in English
- Previous experience as a card recipient
- Currently employed by the VA San Diego

What would being a card recipient entail?

Veterans would receive six cards via mail for six months (one card per month).

All participants will:

- Complete a set of brief baseline and follow-up assessments.
- Be compensated \$60 for each assessment (up to \$120 total).

For more information, please contact [name].

[contact] or [contact]

Email: [contact]

Section 12 - Informed Consent

12) Indicate whether or not each category of consent is involved in this study:

12a) Will the study team obtain information or biospecimens for the purpose of screening, recruiting, or determining the eligibility of prospective subjects without (or prior to) obtaining informed consent of the prospective subject or the prospective subject's LAR?

Yes No

Check one or both of the below boxes if they apply to this study:

Information will be obtained through oral or written communication with the prospective subject or the subject's Legally Authorized Representative (LAR) and this is not a FDA regulated study.

Yes No

Identifiable information or biospecimens will be obtained by accessing records or stored identifiable biospecimens and this is not an FDA regulated study.

Yes No

If either or both of the above boxes is checked "yes", an informed consent waiver does not have to be requested for this activity if the protocol is initially approved after 01/01/2019 or if it has been converted to the 2018 Common Rule requirements. However, a request for a HIPAA waiver will still need to be requested and informed consent obtained for any research interventions after eligibility is established. Otherwise, waivers of consent and authorization must be requested for this activity. Waivers of consent and authorization are required for screening purposes for FDA regulated research.

12b) **Signed** informed consent

Yes No

12c) Waiver of documented consent (e.g., **oral** consent) for all or part of the study.

Yes No

12d) Request for a **waiver** of consent for all or some study activities.

Yes No

12e) Alteration of **other required elements** of consent.

Yes No

12f) **Child** assent to participate (Director approval will be required)

Yes No

12g) Will any language **other than English** be used by those obtaining consent and understood by the prospective participant or the legally authorized representative?

Yes No

12h) **Decisional Capacity Assessment** to determine if participants have the capacity to consent for themselves.

Yes No

12i) **Surrogate** consent (legally authorized representative)

Yes No

Section 12.1 Informed Consent Process

12.1a) Will consent be obtained before any study procedures are performed (including screening procedures except screening procedures with Consent and/or HIPAA waiver when required)?

Yes No

12.1b) Will the information being communicated to the participant or legally authorized representative during the consent process include exculpatory language through which the participant or legally authorized representative is made to waive or appear to waive any of the participant's legal rights or release or appear to release the Researcher, Sponsor, the VA or its agents from liability for negligence.

Yes No

12.1c) A master list of all VA subjects consented (written or not) under this protocol will be maintained.

Agree Disagree

12.1d) Identify the circumstances under which consent will be obtained including where the process will take place; any waiting period between describing the research and obtaining consent including sufficient time for the prospective participant to consider participation, and any steps taken to minimize the possibility of coercion or undue influence.

An introductory letter will be sent to all prospective participants, describing the research (see 11.1 Ads & Flyers for details). Letters to Veterans with inactive HRFs will be sent by the Chief of Psychology, [name], who is a co-I of this project. Letters sent to Veterans with active HRFs will be sent by their Suicide Prevention Coordinators who are in regular contact with HRF Veterans (via phone and mail).

Prospective participants will have approximately two weeks to consider participation. Following two weeks from the date the letter was sent, a member of the research team will reach out to the Veteran via phone to determine if they are interested in being screened for the study. To minimize the possibility of coercion or undue influence, the letters do not guarantee Veterans any direct benefits and clearly state participation in the study is options. There is also information in the letter for Veterans to opt out of being called by a member of the research team, as well as contact information the local Research Compliance Officer, VA Research Service, VA Regional Counsel and the VASDHS Institutional Review Board should they have any questions or concerns about this study or their prospective participation.

For all study prospective participants, after they have been screened, determined to be eligible to participate, and agree to participate, a member of the research team (e.g., study coordinator) will obtain Veterans' consent to participate in the study and assess decisional capacity for informed consent at this time. Consent may be obtained in person (at VA San Diego La Jolla or Rio clinic locations), via phone, WebEx, or VA Video Connect. As previously mentioned, if consent is obtained remotely, we will adhere to current approved guidelines (i.e., use My Health-e-Vet, using MS Azure, have Veteran send signed consent form via email, have Veterans fax, or have the study coordinator take a screen shot of the signed consent during their VVC or WebEx session).

For inpatient prospects, the study coordinator will consult with the PI and/or the Veteran's treating inpatient teams to determine the appropriate timing of approaching Veteran on the unit. If appropriate, the study coordinator will conduct screening on the unit, and if agreeable to participate, consent and baseline assessments may be completed prior to or following discharge.

If a Veteran is conservated, the study coordinator will obtain their conservator's consent for study enrollment, as well as the assent of the conservated Veteran.

Due to the persistence of the COVID-19 pandemic, we plan to enroll participants via telehealth. In our original protocol, we received approval to obtain consents via telehealth. Per our original protocol, "If consent is obtained via phone or VVC, or WebEx, we will adhere to current approved guidelines (i.e., use My Health-e-Vet, using MS Azure, have Veteran send signed consent form via email, have Veterans fax, or have the study coordinator take a screen shot of the signed consent during their VVC or WebEx session)." We would like to amend this approach to include obtaining consent via the WebEx File Transfer feature. Below are the procedures that will be taken to obtain consent via this method.

Webex Consent Appointment (for participant on laptop/computer)

1. Go to your Personal Room by visiting its URL on your computer's browser outside of your remote connection/CAG and click Join Meeting.
 - a. <https://veteransaffairs.webex.com/meet/first.lastname>
2. Go to your Personal Room by visiting its URL on the browser inside your remote connection (CAG).
 3. Allow your outside connection entrance into the meeting
 4. In the WebEx app inside your CAG connection,
 - a. click the red X, select Leave Meeting,
 - b. Select a New Host —> select your outside account

This will transfer hosting privileges to your non-CAG connection and allow you to run the meeting outside of a VA connection.

5. Invite your participant
 - a. Hit button with 3 dots "More options"
 - b. Click "Invite and remind"
 - c. Type in participants email address and hit send
6. Call participant phone-to-phone and help them with downloading process, can let them know they do not need to enable audio or video
7. Obtain location, phone information and emergency contact at start of call
8. Documents to have open inside your citrix desktop
(Fill out participant's name and the date prior to appt.)
 - a. HIPPA
 - i. Need signatures on PAGES 4 & 5
 - b. Informed Consent
 - i. Need signatures on PAGES 5 & 6
 - c. Bill of Rights
 - d. Vendor Form (if participant is not vendorized)
 - e. UBACC

Instructions for sharing inside Citrix

9. After participant joins webex—> RA shares screen from outside of Citrix by clicking "Share Window" and chooses "Citrix Workspace" desktop
 - a. Informed consent & HIPPA inside your Citrix desktop should appear on screen

10. Read through informed consent with participant
11. Conduct UBACC to confirm decisional capacity
12. Once decisional capacity is determined and Veteran agrees to be enrolled, set up the document to allow participant to sign the consent
 - a. Participant will sign and date the consent form by clicking "Sign" on adobe
 - i. This is done by clicking "Add Signature +"
 - ii. Clicking the "Draw" tab
 - iii. Inform them of the slight delay
13. Have participant gain control of the RA's screen

Option 1:

- a. Once sharing your citrix screen, go to orange box on top of the screen and click assign
- b. Choose "Pass keyboard and mouse control"
- c. Choose participant's name

Option 2:

- a. Have participant gain control by clicking "Ask to Control" button in the left-hand side of their screen (2nd button from the top)

14. RA grants control either way
- a. Participant uses their mouse to draw their signature
- b. Participant places their drawn signature on the line on page "Subject's Signature"

15. RA takes back control by going back to the assign button in the orange box and unclicking the participants name/ or having the participant push ESC / or by stopping the screen share
16. RA saves the document into participant folder
17. Read through HIPAA with participant
 - a. Either repeat steps 11-14, or ask permission from participant to use their signature that was saved from their last signature
 - b. Save the form into the participant folder
18. Read through Participant's bill of rights
19. Fill out vendor form with participant *if not vendorized
20. Fill out Screen packet with participant

Inform them of their options to 1) have control shifted to them again so they can fill out the packet on their own, or 2) indicate to the RA which answers to put
21. End screen share
22. Conduct
 - a. Instructions and fillable form open
23. Re-join Webex from inside your citrix connection
 - a. Hit file —> transfer
 - i. Select Informed Consent, HIPAA, and Bill of Rights over to participant
 - ii. Have them click on each file and hit "Download"
24. End Appointment

If participant is using phone or tablet:

Follow steps 1-12 above, then

13. Have participant click the "annotate" option. (it is a squiggly line button for them)
14. Have participant adjust width and color of the pen tool and then draw their signature and place it onto appropriate areas
15. Ensure a blank word document is open and that the page you are screenshotting is zoomed to view entire page

PC: Take a screenshot by hitting "Print Screen" and have screenshot appear in the word document, can save as pdf, crop the sides, and combine into original consent or HIPAA materials

MAC:

- a. From inside citrix, ensure that your WebEx screen shows the adobe document
- i. Go into that word document
- ii. Hit insert —> Screenshot —> screen clipping
- iii. Take screen clipping of desired page
- iv. Ensure screen clipping inserts into the open word document
- v. Can save as pdf, crop the sides, and combine into original consent or HIPAA materials

16. Complete these steps for necessary pages in both HIPAA and Consent Packet, ensuring to review with participant. Resume @ step 17
17. Print out and mail informed consent documents

—
The study investigators are requesting to use DocuSign (eSig) to consent participants. We received approval to use DocuSign (eSig) by ORD on 2/3/2021.

ORD is providing us with 150 envelopes for this study. We've been instructed to work with our local IRB/research office to integrate the SOPs, which have been sent to the IRB team, into the local processes. I have corresponded with [name] about next steps for setting up this process.

Below are the steps the research team will take to use DocuSign (eSig) to consent participants:

- 1) Potential subjects will be mailed our IRB approved introductory letter explaining the study and providing a study staff contact phone number. (These letters have already been IRB approved for both card makers and recipients).
- 2) During the screening phone call with the potential subject (scripts have already been IRB approved), if the potential subject screens eligible and is interested in learning more about the study, the study team member will schedule a time to go over study documents (Informed Consent Form and HIPAA Authorization [or combined ICF/HIPAA]) using DocuSign.
- 3) At the time of remote consenting, the study team member/conserver will send a DocuSign envelope (email containing links to the study documents) to the potential subject. The email will contain a reminder for the recipient to not sign the documents prior to the scheduled contact time. (See "Email Script" and "Stand Alone eSig service SOP," section 3 [attached and highlighted for reference]).
- 4) At the scheduled time, the study team member (referred to as "conserver") will contact the potential subject via phone, VA Video Connect (VVC), or other approved secure communication method (i.e., WebEx). The conserver will guide the potential subject to open the DocuSign envelope (email) and the linked study documents therein. The conserver will open a copy of the study documents on their own computer as a reference. The conserver will review the study documents with the potential subject, ask questions to gauge comprehension, and answer any questions and concerns. If the potential subject agrees to participate in the study, the conserver will guide them to fill in the fields in the study documents (e.g., "Last, First, Middle Initial" name field, Last 4 SSN field, etc.) and to sign the documents. When the subject has signed the documents, they will click "FINISH" to finalize the documents.
- 5) While still on the phone/VVC (or other approved secure communication method, i.e., WebEx) with the subject, the conserver will receive an email notification to log into DocuSign. The conserver will verify that all fields are completed accurately and, if necessary, subsequently sign the document(s) (e.g., ICF). The conserver will guide the subject on how to download a copy (ies) of the signed document(s) to the subject's personal computer for their record. The conserver will thank the subject and end the call.
- 6) The conserver will download a copy(ies) of the signed document(s) (see "Stand Alone eSig service SOP," section 3) to a study folder in VA network drive (i.e., R:\[name]) as study record. If necessary, the conserver can sign the ICF and save it back to this folder. The conserver will also place another copy(ies) of the signed document(s) in another study-specific folder (e.g. W:\) for HIMS to upload the documents into Electronic Health Record (EHR; i.e., VistA/CPRS or Cerner) (or other ways as agreed upon by local HIMS). The conserver should notify HIMS that the documents need to be placed in the EHR (per local agreement). The conserver will then check the EHR one week later to ensure the documents have been uploaded. If the documents have been uploaded, the conserver will remove the documents from the W:\ drive. If the documents have not been uploaded within one week, the conserver will re-notify HIMS to upload the documents into the EHR.
- 7) The conserver will document the consenting process as a "Research/Informed Consent" note in the subject's medical record (in CPRS). The note will specify that consent was obtained over phone/VVC/WebEx and DocuSign on the specific date. HIMS will attach the signed documents to this note.

Section 12.6 Decisional Capacity Assessment

12.6a) Describe the method(s) for determination of decisional capacity: (see ? for guidance) *Please note that documentation of the assessment is required.*

Participants must have decisional capacity for informed consent in order to meet eligibility for this study. To ensure this, the University of California San Diego Brief Assessment of Capacity to Consent (UBACC) will be used. The UBACC is a 10-item questionnaire tailored to specific study procedures. It queries participants about the basic procedures, risks, benefits, and purpose of the study, along with participant rights. Each item on the UBACC is scored on a 0 (incapable) to 2 (capable) scale. This will be administered at the time of obtaining informed consent.

The following are the questions and answers to this study's UBACC for card makers and recipients:

Card Makers:

1. What is the purpose of the study that was just described to you?
 - a. Response (2 = Study about Veterans making and receiving cards for suicide prevention and/or social connection)
2. What makes you want to consider participating in this study?
 - a. Response (2 = Increased social connection, help others, decreased suicide risk/behaviors)
3. Do you believe this is primarily research or primarily treatment?
 - a. Response (2 = Research)
4. Do you have to be in this study if you do not want to participate?
 - a. Response (2 = No)
5. If you withdraw from this study, will you still be able to receive regular treatment?
 - a. Response (2 = Yes)
6. If you participate in this study, what are some of the things that you will be asked to do?
 - a. Response (2 = Answer questions and attend a weekly card making group)
7. Please describe some of the risks or discomforts that people may experience if they participate in this study.
 - a. Response (2 = Feeling bored or fatigued, feeling anxious or discomfort while talking about myself and/or symptoms, feeling uncomfortable drawing upon my lived mental health experience to create caring cards for other Veterans in need.)
8. Please describe some of the possible benefits of this study.
 - a. Response (2 = Increased social connectedness and sense of purpose, help others, decreased suicide risk and related behaviors).
9. Is it possible that being in this study will not have any benefit to you?
 - a. Response (2 = Yes)
10. Who will pay for your medical care if you are injured as a direct result of participating in this study?
 - a. Response (2 = VA San Diego)

Card Recipients:

1. What is the purpose of the study that was just described to you?
 - a. Response (2 = Study about Veterans making and receiving cards for suicide prevention and/or social connection)
2. What makes you want to consider participating in this study?
 - a. Response (2 = Increased social connection, decreased suicide risk/behaviors)
3. Do you believe this is primarily research or primarily treatment?
 - a. Response (2 = Research)
4. Do you have to be in this study if you do not want to participate?
 - a. Response (2 = No)
5. If you withdraw from this study, will you still be able to receive regular treatment?
 - a. Response (2 = Yes)
6. If you participate in this study, what are some of the things that you will be asked to do?
 - a. Response (2 = Answer questions and receive cards)
7. Please describe some of the risks or discomforts that people may experience if they participate in this study.
 - a. Response (2 = Feeling bored or fatigued, feeling anxious or discomfort while talking about myself and/or symptoms, feeling uncomfortable receiving cards that might remind me of my symptoms)
8. Please describe some of the possible benefits of this study.
 - a. Response (2 = Increased social connectedness, decreased suicide risk and related behaviors).
9. Is it possible that being in this study will not have any benefit to you?
 - a. Response (2 = Yes)
10. Who will pay for your medical care if you are injured as a direct result of participating in this study?
 - a. Response (2 = VA San Diego)

12.6b) If subjects with limited decisional capacity will be enrolled, describe methods for obtaining subject assent or why they are not indicated:

Participants with limited decisional capacity will not be enrolled.

12.6c) If subjects with limited decisional capacity will be enrolled, describe procedures for respecting subject dissent and any additional safeguards or why these features are not needed:

Participants with limited decisional capacity will not be enrolled.

12.6d) If subjects with limited decisional capacity will be enrolled, describe the risk and, if greater than minimal, the relation to potential benefits:

Participants with limited decisional capacity will not be enrolled.

12.6e) If subjects with limited decisional capacity will be enrolled, describe the justification for the inclusion of any incompetent persons or persons with impaired decision-making capacity:

Participants with limited decisional capacity will not be enrolled.

Section 12.7 Consent by Legally Authorized Representative (Surrogate Consent)

12.7a) Where endorsed by the IRB, the following persons may be authorized to consent on behalf of persons who lack decision-making capacity in the indicated order of priority: (a) Health care agent (i.e., an individual named by the individual in a Durable Power of Attorney for Health Care (38 CFR.17.32(a)(iii)); (b) Legal guardian or special guardian; (c) Next of kin in this order: a close relative of the patient 18 years of age or older, in the following priority: spouse, child, parent, sibling, grandparent, or grandchild; (d) A close friend [however, California Health and Safety Code §24178 does NOT include the close friend category]

Agree Disagree

